7.4 Pharmacodynamics

Mandatory samples (unless technically not possible) for pharmacodynamic (PD) assessment will be taken as follows:

- At screening (within 28 days prior to DTP3 treatment)
- **24 hours** (range 18-36 hr) after the **fourth dose** of DTP3 treatment (Cycle 1, Week 2, Day 2)

Tissue will be collected as follows on each occasion for PD, genetic and biomarker assessment and sent in their entirety to the Hammersmith site ([name] lab):

- MM: 50 mL of blood and 10 mL of bone marrow aspirate
- DLBCL: 50mL of blood and a tumour biopsy (18G core), if accessible.

7.5 *Efficacy* Assessments

7.5.1 MM

Routine efficacy assessments will be performed every 4 WEEKS (see Trial Assessment Schedule, Appendix C) unless clinically indicated at an earlier time point. The following assessments will be performed on a 4-weekly basis:

- Serum protein electrophoresis and paraprotein quantification
- Serum free light chain
- 24h urine collection electrophoresis (only in patients with detectable urinary M protein at screening)
- Biochemistry panel
- Full Blood Count

The necessity for bone marrow aspirate and biopsy and/or radiological imaging will be determined by the patient's individual clinical course and will only be undertaken when judged appropriate by the investigator for determination of response or progression, as follows:

If a complete (or stringent complete) response is suspected:

Two independent measurements (according to normal institutional practice) are required to confirm:

- negative immunofixation: serum
- negative immunofixation: urine

If these two independent measurements are consistent with the definition of a complete response, then a bone marrow aspirate and biopsy should be performed

If progression is suspected:

This can be determined by measurement of any relevant disease parameter, including radiological imaging and/or bone marrow plasma cell percentage, but should be confirmed by two independent measurements, according to normal institutional practice.

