8.2 Analysis Sets

Three study populations will be defined:

- Three study analysis sets will be defined:
- **The safety analysis set** will be used as the analysis population for all safety endpoints and comprises all patients who receive at least one dose of DTP3.
- **The efficacy analysis set** will include all patients who receive at least one dose of DTP3 and will be used as the analysis population for efficacy endpoints.
- **The per protocol analysis set** will be used as a sensitivity analysis for efficacy and pharmacodynamic endpoints and comprises patients who:

- The **per protocol analysis set** will be used as a sensitivity analysis for efficacy and pharmacodynamic endpoints and comprises patients who:
 - Fulfil all the inclusion and none of the exclusion criteria
 - Received at least 2 cycles of DTP3 (*i.e.* ≥8 weeks of therapy) or have documented progression at an earlier time point.
- Have at least one efficacy assessment undertaken after ≥8 weeks of therapy or have documented progression at an earlier time point.
- Have completed PD blood and bone marrow (MM) /tumour (DLBCL) sampling (after seventh dose of DTP3)

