Calculated creatinine clearance	×	^				^			^				^		
Pregnancy serum (where appropriate)	×												l	l	
PT and APTT (coagulation testing)	x								l					l	
Full Blood Count (Haematology)															
Haemoglobin	x	×				×			×				x		
Hematocrit	x	×				x			×				x		
WBC count with complete manual or automated differential	x	×				x			x				x		
RBC count	x	×				×			×				×		
Platelet count Biochemistry assessment	×	×				×			×				×		
Renal Profile (Sodium, Potassium, Creatinine, Urea, eGFR, blood															
urea nitrogen)	×	×				×			×				×		
Calcium (bone profile)	x	×				x			x				x		
Uric acid	x	×				x			x				х		
Lactate dehydrogenase	x	×				x			x				x		
Chloride	x	×				x			×				х		
Bicarbonate	x	×			L	×			x				x	l	
Glucose LFT (ALT, ALP, Total Bilirubin, Albumin, Total protein, Globulin, AST)	×	×				x			×				×	l	
Phosphorous	×	×	l			×			×				×	l	
DTP3	^	· · ·				 			~				-		
IMP administration		×		×	x	×	×	×	×		×	×	x	x	x
PK															
4ml blood sample		X*	Xª	Xe	Xp										
MULTIPLE MYELOMA PATIENTS:															
MM specific assessments															
Serum protein electrophoresis (SPEP)	x														
Paraprotein quantification Serum immunofixation	x														
Serum immunoglobulin levels	x													-	
Serum free light chains (sFLC)	x														
24-hour urine sample for urine proteins and urine immunofixation	×														
FDG-PET/CT, whole body MRI, or whole body low-dose CT (unless performed within 8 weeks of treatment starting)	×														
Bone marrow aspirate and biopsy for local determination of															
plasma cell count	×														
Beta-2 microglobulin level	x														
MM - PD, lab and genetic assessments															
Bone marrow 10mL aspirate	×									Xe				l	
50ml blood sample DIFFUSE LARGE B-CELL LYMPHOMA PATIENTS:	×									X-					
DIFFUSE LARGE B-CELL LYMPHOMA PATIENTS: DLBCL specific assessments ¹															
FDG-PET/CT (unless performed within 4 weeks of treatment															
starting)	×														
Bone marrow aspirate and biopsy [for histological evaluation of DLBCL involvement]	×														
DLBCL - PD, lab and genetic assessments	^														
	x									Xc					
Tumour sample (where accessbile)										Xc				1	1

			EXPANS	GION STA	GE							
							LE 2					

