	points idealy within +/- 2 minutes. For samples taken after the first hour, there can be a
	small window of +/- 5 minutes, for samples taken at 12 hours and later a window of 30
	minutes is allowed. The exact time of bleeding will anyway be registered on the log.
b	Pre infusion, 0.5hr, 1hr,2hr and 4hr (post-infusion)
	These samples will be collected 24 hours (range 18-36 hours) after completion of
	administration of the FOURTH dose of DTP3.
c	Further samples will be collected if a complete response is suspected or clinically required
	as determined by the Investigator
d	Patients receiving DTP3 after cycle 3 will continue with the assessments scheduled as per
-	cycle 3
	Dose Escalation Stage:
	Week 1 and 2: During Cycle 1, BP, pulse rate and 12 lead ECG will be carried out 15 min
	before and 30 mins, 60 min and 120 min after end of each DTP3 infusion (+/- 5mins).
	Week 3 and 4. During Cycle 1, BP, pulse rate and 12 lead ECG will be carried out 15 min before and 30 mins after end of each DTP3 infusion (+/- 5mins).
	Cycle 2-onwards : BP, pulse rate and 12 lead ECG will be carried out 15 min before and 30
	mins after end of each DTP3 infusion (+/- 5mins).
e	Cohort Expansion Stage:
	Week 1: During Cycle 1, BP, pulse rate and 12 lead ECG will be carried out 15 min before
	and 30 mins, after end of each DTP3 infusion.
	Week 2 onwards : BP, pulse rate and 12 lead ECG will be carried out before the first dose
	of DTP3 at the beginning of week 2 onwards (eg. before dose 4,7,10 etc)
f	Only to be done on a monthly basis in patients with detectable urinary M protein at
	screening
g	Pre-infusion
h	Bone marrow aspirate and biopsy required if radiological complete response
-	Serum pregnancy test (where appropriate) at beginning of each cycle of DTP3 and then
i	monthly for six months after cessation of DTP3 therapy.
j	To continue 8 weekly for evaluation as long as participating
	Where this is no Disease Progression when ceasing DTP3 treatment, survival status to
	continue being recorded for a period of six months after the last patient has been
k	recruited into the study. Via clinic team if under their care, or six weekly via family
	member.
1	Possible tests pending patient outcome of disease progression or complete resolution and
	local institutional practice:
	If at any point, a complete reponse is suspected in a patient, they will undergo:
	MM:
	 Two independent measurements (according to normal institutional practice)
	confirming:
	-negative immunofixation serum

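### Section 8.2 ties the per-protocol set to PD tissue after the seventh dose, while the protocol text samples after the fourth and the two Appendix C grids disagree

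*Protocol*

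**What the plan says.** **Per-protocol set (Section 8.2).** The set "will be used as a sensitivity analysis for efficacy and pharmacodynamic endpoints". Membership requires eligibility, two cycles of DTP3 or earlier documented progression, an efficacy assessment after at least 8 weeks or earlier documented progression, and that patients "Have completed PD blood and bone marrow (MM) /tumour (DLBCL) sampling (after seventh dose of DTP3").

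**Main efficacy set (Section 8.2).** This set "will include all patients who receive at least one dose of DTP3 and will be used as the analysis population for efficacy endpoints". It carries no PD condition.

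**Sampling time in the text.** Section 7.4, the synopsis and Section 3.1 agree: 24 h (range 18 to 36 h) after the fourth dose "of DTP3 treatment (Cycle 1, Week 2, Day 2"). Samples are mandatory unless technically not possible. The DLBCL biopsy is taken only if the tumour is accessible.

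**Appendix C.** Key c times the samples after "administration of the FOURTH dose of DTP3". It adds: "Further samples will be collected if a complete response is suspected or clinically required". The escalation grid marks the row "Bone marrow 10mL aspirate" at Week 2 Day 2. The expansion grid has no Week 2 Day 2 column in Cycle 1. It marks the same row at Week 3 Day 2, between Dose 7 and Dose 8, and its DLBCL sample marks carry key c.

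**Pooling.** Sections 5.2 and 8.3 count escalation patients dosed at the RP2D in the expansion analysis.

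**The concern.** Section 8.2 and the expansion grid point to the seventh dose. Every narrative statement of the schedule, key c and the escalation grid point to the fourth. Membership of the per-protocol set therefore depends on which page a site follows. Sites working from different pages would also produce on-treatment tissue from different points in treatment, in a study where PD response and its correlation with GADD45β expression are secondary endpoints.

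A second problem would remain even with the time point settled. The per-protocol set serves efficacy as well as PD. Two of its bullets deliberately keep patients with early documented progression, and the PD bullet takes out those who progress before the sample is due. A sensitivity analysis that loses early failures tests robustness in the favourable direction only.

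**Working it through.** **1. Reproduce the plan's own calendar position.** Doses fall on Days 1, 3 and 5 of each week (Appendix C).
- Dose 4 = study day 8 = Week 2 Day 1. Adding 24 h gives Week 2 Day 2, as Section 7.4 states.
- Dose 7 = study day 15 = Week 3 Day 1. Adding 24 h gives Week 3 Day 2, the column marked in the expansion grid.

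**2. Can one sample satisfy both?** The nominal gap is (15 − 8) × 24 = 168 h. Section 5.1 allows inter-dose intervals of 40 to 72 h, and three intervals separate doses 4 and 7, so the shortest permitted gap is 3 × 40 = 120 h. The sampling window closes 36 h after dose 4. A sample taken inside it cannot be a post-dose-7 sample.

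**3. Set the sources side by side.**

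| Source | On-treatment PD sample |
|---|---|
| Synopsis, 3.1, 7.4 | after dose 4, Week 2 Day 2 |
| Appendix C key c | after dose 4 |
| Appendix C escalation grid | Week 2 Day 2 (after dose 4) |
| Appendix C expansion grid | Week 3 Day 2 (after dose 7) |
| 8.2 per-protocol criterion | after dose 7 |

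Grid positions come from counting columns after the screening mark. The sixth in the escalation grid is Week 2 Day 2, and the ninth in the expansion grid is Week 3 Day 2.

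**4. Follow each reading through to the per-protocol set.**
- Text and key c followed in both stages: no routine sample meets the criterion, so the set has no routine members.
- Each stage follows its own grid: expansion patients can qualify. Routinely sampled escalation patients cannot, including any RP2D patients pooled into the expansion analysis. On-treatment PD data then combine samples after four and after seven doses.
- Sites differ: membership varies by site for reasons unrelated to adherence.

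**5. Direction of the effect on ORR.** Treatment stops at progression (Section 5), and the first scheduled response assessment is at 4 weeks (MM) or 8 weeks (DLBCL). A patient who progresses and stops before the sample has therefore had no scheduled assessment at which to respond, and would count as a non-responder. Let x be the number of responders among n patients who meet the other per-protocol bullets, and k the number of early progressors removed. The estimate moves from x/n to x/(n − k), which is larger whenever x > 0 and k > 0. The protocol gives no value for k. As an illustration only, take its observed rate of 41.7% as 10/24 and assume k = 1 to 3:
- k = 1: 10/23 = 43.5%
- k = 2: 10/22 = 45.5%
- k = 3: 10/21 = 47.6%

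**The case against.** The strongest reply is that little depends on this set. It is a sensitivity population, and the primary ORR, the 25% threshold and the safety analyses use no PD condition. PD data are summarised descriptively. Section 8 makes the SAP the definitive reference and lets it modify the analysis plan. All of this stands and limits the severity. But a SAP can redefine a set; it cannot re-time marrow or tumour tissue already taken, or correct the grid that sites use.

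The column positions come from text extracted from a PDF. One weight mark in the expansion grid looks misplaced, and the MM sample marks do not legibly carry key c. The positions should be checked against the original table. The reading does not rest on them alone: the expansion header has no Week 2 Day 2 column and has a non-dosing column between Dose 7 and Dose 8.

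On mixed exposure, Sections 1.2 and 1.3 report no accumulation on repeated dosing, so plasma levels around doses 4 and 7 may be similar. Section 1.2 also reports greater apoptosis in vitro after repeated administration, so similar plasma levels do not guarantee comparable PD readings.

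Requiring a mandatory procedure for per-protocol status is common and not an error in itself. That holds for a PD analysis. For efficacy, the requirement conflicts with the bullets that keep early progressors.

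Three stronger readings are tempting and not supported:
- **That the set would contain nobody.** The expansion grid satisfies the seventh-dose condition, and key c allows later samples.
- **That all six or more patients treated at the RP2D before expansion would be pooled and then lost.** The synopsis and Section 5.2 pool DLBCL patients only if non-GCB, so the pooled number may be smaller.
- **That response would be re-estimated only in patients whose tumour can be biopsied.** MM patients give marrow. For DLBCL, completed sampling may mean whatever sampling the protocol required of that patient.

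**Conclusion.** Wrong as written. The protocol holds two on-treatment PD sampling times, 168 h apart on the nominal calendar, and the per-protocol criterion uses the one that the text, key c and the escalation grid do not. Depending on which source is followed, either no routine sample qualifies anyone, or routinely sampled escalation patients fail and PD data from two points in treatment are combined. This rests on the criterion being applied literally and on no additional sample being taken later under key c.

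Separately, the PD condition removes early progressors from the efficacy sensitivity analysis and can push its ORR upward. The size depends on how many there are, which the protocol does not state. DLBCL patients without an accessible tumour may also be lost, depending on how completion is read.

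Severity is moderate: only the sensitivity and PD analyses are affected.

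**What to change.** 1. Reconcile Section 8.2, Section 3.1, Section 7.4, the synopsis, key c and both Appendix C grids on a single PD sampling time point, before expansion sampling. Which time point applies is for the sponsor to decide.
2. Take the PD-sampling condition out of the per-protocol set used for efficacy.
3. Define a separate PD-evaluable set for the PD analyses: patients with a screening sample and an on-treatment sample at the agreed time point. State how a DLBCL patient with no accessible tumour, or a patient whose sample was technically not possible, is classified.
4. If samples have already been taken at both times, record the dose number for each and present PD results separately by it.

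The cost is amendment wording and a corrected schedule table, with no extra procedure for patients. The value falls once invasive samples have been taken at inconsistent times, because they cannot be repeated retrospectively.

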In vitro studies in MM serial cell lines and primary MM *ex vivo* patient cells demonstrated a clear induction of cell death by apoptosis at doses of DTP3 in the low nanomolar to low micromolar ^{Error1 Reference source not found.} Treated cells were also analysed by western blot and flow cytometry, with results showing that a single administration of DTP3 was effective in inducing JNK activation and that this activity was maintained at least up to 24 hr but lost by 48 hrs. Repeated administration of DTP3 resulted in greater apoptosis as compared to single treatment. Similarly, JNK and caspase 3 (measures of pathway engagement and apoptosis) were strongly activated by multiple administrations of DTP3. Notably, DTP3 retained full therapeutic efficacy in MM cells that are resistant to most conventional MM treatments, which could be of major clinical significance, as nearly all patients will eventually relapse and/or develop drug resistance^{43,44}.

The analysis of DLBCL datasets from patients demonstrated that GADD45 β expression correlated with the NF- κ B target gene signature and shorter overall survival (OS) following treatment with CHOP-like or Rituximab-CHOP-like therapy. Studies in DLBCL cell lines demonstrated that GADD45 β is preferentially (albeit not exclusively) expressed in ABC (non-GCB) relative to GCB cell lines. In agreement with these data, *in vitro* studies of DTP3 in DLBCL serial cell lines and primary *ex vivo* DLBCL patient cells demonstrated a selective induction of JNK activation and apoptosis in most cells exhibiting elevated GADD454 β expression, when analysed by western blot or flow cytometry. These effects resulted in a clear induction of cell death at doses of DTP3 in the nanomolar to low micromolar range. Notably, DTP3 retained full therapeutic efficacy in DLBCL cells resistant to ibrutinib and/or idelalisib, two drugs widely used for the treatment of DLBCL.

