*A score of 3 in many patients indicates a good prognosis with standard treatment, especially if at the time of an interim scan. However, in trials involving PET where de-escalation is investigated, it may be preferable to consider a score of 3 as inadequate response (to avoid undertreatment). Measured dominant lesions: Up to six of the largest dominant nodes, nodal masses, and extra-nodal lesions selected to be clearly measurable in two diameters. Nodes should preferably be from disparate regions of the body and should include, where applicable, mediastinal and retroperitoneal areas. Non-nodal lesions include those in solid organs (eg, liver, spleen, kidneys, lungs), GI involvement, cutaneous lesions, or those noted on palpation. Non-measured lesions: Any disease not selected as measured, dominant disease and truly assessable disease should be considered not measured. These sites include any nodes, nodal masses, and extra-nodal sites not selected as dominant or measurable or that do not meet the requirements for measurability but are still considered abnormal, as well as truly assessable disease, which is any site of suspected disease that would be difficult to follow quantitatively with measurement, including pleural effusions, ascites, bone lesions, leptomeningeal disease, abdominal masses, and other lesions that cannot be confirmed and followed by imaging. In Waldeyer's ring or in extranodal sites (eg, GI tract, liver, bone marrow), FDG uptake may be greater than in the mediastinum with complete metabolic response, but should be no higher than surrounding normal physiologic uptake (eg, with marrow activation as a result of chemotherapy or myeloid growth factors). †PET 5PS: 1, no uptake above background; 2 uptake ≤mediastinum; 3, uptake > mediastinum but ≤ liver; 4, uptake moderately > liver; 5, uptake markedly higher than liver and/or new lesions; X, new areas of uptake unlikely to be related to lymphoma.

APPENDIX C: Trial Assessment Schedule for Patients in the Dose Escalation and Cohort Expansion Stages

					ESCALA	TION STAGE										
				_			_	_	CYCLE 1		_			_	_	
	Within 28		Week 1 Day			Week 2 Day	Week 2 Day	Week 2 Day			Week 3 Day	Week 3 Day	Week 3 Day	Week 4 Day		
	days prior to first dose	1 Dose 1	2 N/A	3 Dose 2	5 Dose 3	1 Dose 4	2 N/A	3 Dose 5	5 Dose 6	1 Dose 7	2 N/A	3 Dose 8	5 Dose 9	1 Dose 10	3 Dose 11	5 Dose 12
Initial tests	to first dose	Dose 1	N/A	Dose 2	Dose 3	Dose 4	N/A	Dose 5	Dose 6	Dose /	N/A	Dose 8	Dose 9	Dose 10	Dose 11	Dose 12

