Globulin, AST)	×											
Phosphorous	×		l	l	l							
DTP3												
IMP administration	×	×	×	×	×	×	×	×	×	×	×	×
PK												
4ml blood sample												
MULTIPLE MYELOMA PATIENTS:												
Myeloma-specific assessments												
Serum protein electrophoresis (SPEP)	×											
Paraprotein quantification	x x									l		
Serum immunofixation	1	i	1	1	1							1
Serum immunoglobulin levels	1		1	1						I		
Serum free light chains (sFLC)	×											
24-hour urine sample for urine proteins and urine												
immunofixation ⁶	×											
FDG-PET/CT whole body MRI, or whole body low-dose CT												
(unless performed within 8 weeks of treatment starting)	I		L	L	L				└──── ┘	L	L	I
Bone marrow aspirate and biopsy for local determination of plasma cell count	1		1	1	1				1	1	1	1
Beta-2 microglobulin level	1		I		l				 	H	L	t
MM - PD, lab and genetic assessments												
Bone marrow 10mL aspirate	1											
50ml blood sample	1		1	1	l				L	l		1
DIFFUSE LARGE B-CELL LYMPHOMA PATIENTS:												
DLBCL specific assessments "												
FDG-PET/CT ¹	× ⁱ											
Bone marrow aspirate and biopsy [for histological evaluation	 		l		l				t'	H	L	t
of DLBCL involvement] *	1		1	1					1	1 /	1	1
PD, lab and genetic assessments												
Tumour sample (where accessbile)	1											
50ml blood sample	1	I	I						t'	•	l	 

Protocol – DTP3 v.4.0 12-Dec-2023

				E	XPANSION S	TAGE									
								CYC	LE 1						
	Within 28	Week 1	Week 1	Week 1	Week 1	Week 2	Week 2	Week 2	Week 3	Week 3	Week 3	Week 3	Week 4	Week 4	Week 4
	days prior	Day 1	Day 2	Day 3	Day 5	Day 1	Day 3	Day 5	Day 1	Day 2	Day 3	Day 5	Day 1	Day 3	Day 5
	to first dose	Dose 1	N/A	Dose 2	Dose 3	Dose 4	Dose 5	Dose 6	Dose 7	N/A	Dose 8	Dose 9	Dose 10	Dose 11	Dose 12
Initial tests	0010														
Written informed consent	x														
Medical history	x														
Disease specific history (MM/DLBCL)	x														
ECOG Performance Status	×							×							×
Adverse Events Concomitant medications	×	x		×	x	x	x	×	x		x	×	x	x	×
Physical examination (as per local clinical standards and as	^				 		^	 	 				 	 	^
considered adequate by the PI)	x														
Height	x														
Weight	×	xm			x'''				×"				x ^m		
Blood pressure	x	Xe		Xe	Xe	Xe	Xe	Xe	Xe		Xe	Xe	Xe	Xe	Xe
Pulse rate	x	Xe		Xe	Xe	Xe	Xe	Xe	Xe		Xe	Xe	Xe	Xe	Xe
Respiratory Rate	x	Xe	l	Xe	Xe	X*	Xe	X*	X*		Xe	Xe	Xe	Xe	Xe
12-lead ECG Urinalsyis	x	×		X-	X-	×	×-	X-	×		X-	X-	×	X-	X-

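### The on-treatment PD sample is set after Dose 4 in the text but after Dose 7 in the expansion grid and in the per-protocol definition, so that sensitivity set can be empty or lose every escalation patient

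*Protocol*

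**What the plan says.** **Sampling after the fourth dose.** Section 7.4 fixes the mandatory on-treatment sample at 24 hours, "range 18-36 hr) after the fourth dose of DTP3 treatment (Cycle 1, Week 2, Day 2". The synopsis and Section 3.1 say the same, and none of the three distinguishes escalation from expansion. Key c of Appendix C times the sample from "administration of the FOURTH dose of DTP3". In the escalation Cycle 1 grid the header reads "Dose 4 N/A Dose 5", and the on-treatment marrow, blood and tumour marks belong to that non-dosing day, Week 2 Day 2.

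**Sampling after the seventh dose.** The expansion Cycle 1 header reads "Dose 4 Dose 5 Dose 6 Dose 7 N/A Dose 8". It has no Week 2 Day 2 column, and the on-treatment PD marks stand in the non-dosing column after Dose 7, Week 3 Day 2. Section 8.2 makes it a condition of the per-protocol set that patients "Have completed PD blood and bone marrow (MM) /tumour (DLBCL) sampling (after seventh dose of DTP3".

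**Use of the data.** Section 8.2 names the per-protocol set as the sensitivity population for both efficacy and PD. The main efficacy set is everyone dosed at least once. Section 8.3 summarises PD by dose level and disease cohort, and lets escalation patients treated at the recommended Phase 2 dose (RP2D) count towards the expansion stage.

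**The concern.** A patient sampled exactly as Section 7.4 instructs has no scheduled sample after Dose 7 and, read literally, cannot enter the per-protocol set. A patient sampled as the expansion grid shows can enter it, but has been sampled outside the window in Section 7.4 and key c. The protocol therefore does not tell an expansion site which day is correct, and it defines an analysis set by a sample that most of its own text never schedules.

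Two things are at stake. One is whether the named sensitivity analysis for response can be run at all, and on whom. The other is whether PD results at the RP2D describe one time point or two. Section 8 lets the statistical analysis plan (SAP) modify the analyses, so the set definition can still be repaired there. A marrow aspirate or tumour core taken on the wrong day cannot.

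**Working it through.** **1. The protocol's own precision figure.** Section 8.1 gives a one-sided 90% Clopper-Pearson lower limit of 27.7% at an observed 41.7%, with 24 patients per cohort. The limit is the 0.10 quantile of Beta(x, n − x + 1). With x = 10 and n = 24 (10/24 = 41.7%), Beta(10, 15) gives 27.72%, which reproduces the figure. It belongs to the primary response analysis and does not depend on the PD sampling day.

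**2. Calendar.** Dosing is on Days 1, 3 and 5 of each week, so study day = 7 × (week − 1) + day.

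- Dose 4 (Week 2 Day 1): 7 + 1 = day 8.
- Dose 7 (Week 3 Day 1): 14 + 1 = day 15.
- Week 2 Day 2: 7 + 2 = day 9.
- Week 3 Day 2: 14 + 2 = day 16.

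| Sampling day | Hours after Dose 4 | Relative to Dose 7 |
|---|---|---|
| Day 9 (text, key c, escalation grid) | (9 − 8) × 24 = 24 | (15 − 9) × 24 = 144 h before |
| Day 16 (expansion grid) | (16 − 8) × 24 = 192 | (16 − 15) × 24 = 24 h after |

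The window is 18 to 36 hours after Dose 4. Day 16 overshoots its upper end by 192 − 36 = 156 hours, so no single sample can satisfy both the expansion grid and key c. No sample on day 9 can satisfy Section 8.2.

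**3. Is it a table-reading artefact?** Counting columns after screening, the escalation mark is in the sixth (Week 2 Day 2) and the expansion mark in the ninth (Week 3 Day 2). The expansion header lists the doses in order with no gap between Doses 4 and 7, and Section 8.2 writes the seventh dose out in prose. The superscripts on the expansion myeloma marks are not reliably legible in the text available. Those on the DLBCL marks read c, so a mark placed after Dose 7 cites a key that says fourth dose.

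**4. Who can meet the Section 8.2 condition.**

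- *Text and key c followed in both stages:* no scheduled sample falls after Dose 7, so 0 of 24 per cohort qualify. Key c allows further samples at suspected complete response or on clinical need. These could fall after Dose 7, but a set built from them could select on outcome.
- *Grids followed:* escalation patients are sampled on day 9 and all fail; expansion patients can qualify. The protocol requires at least six patients, both diseases together, at the RP2D before expansion. It does not say how many will fall in each cohort. Assuming that e of a cohort's 24 come from escalation, at most 24 − e qualify: 24 for e = 0, 21 for e = 3, 18 for e = 6. The RP2D summary for that cohort then combines e samples from day 9 with 24 − e from day 16.

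The two outcomes are alternatives and cannot both occur in full. Sites that differ in practice would produce something in between.

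**The case against.** The strongest reply is that nothing primary is affected. Response is analysed in all dosed patients, the 27.7% limit stands, PD is secondary and descriptive, and the SAP may redefine the per-protocol set. All of that is correct and limits the severity. What remains is the sampling instruction itself, which the SAP cannot repair after the sample has been taken.

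Three stronger readings are tempting, and the protocol does not support them.

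- *That the RP2D decision is compromised.* The RP2D is chosen from escalation data, where text, key and grid agree on Dose 4. Section 5.4 adds that, once the RP2D has been set early, findings from continued escalation do not reopen it. The Dose 7 mark appears only in the expansion grid.
- *That the markers are known to differ between the two days.* Section 1.2 does say "Repeated administration of DTP3 resulted in greater apoptosis as compared to single treatment", but that is in vitro and compares repeated with single dosing, not four doses with seven. Both candidate samples fall 24 hours after a dose, and the earlier patient study found no accumulation. A time effect is plausible but not shown, and no comparison between stages is planned.
- *That the whole study would contribute no per-protocol patients.* This holds only if every site follows the text and no unscheduled sample is counted. A study-wide count would also need a ceiling, for which the synopsis gives 85 and Section 4.4 gives 72.

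It could also be said that Section 8.2 and the expansion grid agree with each other, so Dose 7 may be what was intended. That is a reason to ask the sponsor, not to assume either answer.

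**Conclusion.** The contradiction is real and should be fixed. Read literally, the per-protocol set contains 0 of 24 patients per cohort if sites follow the text, apart from any with unscheduled samples. If sites follow the grids it contains at most 24, 21 or 18 of 24, assuming 0, 3 or 6 pooled escalation patients, and RP2D-level PD summaries can mix day 9 with day 16.

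The conclusion rests on a literal reading of Section 8.2, on dosing without delay on Days 1, 3 and 5, and on the assumed split of escalation patients. A reader might infer a threat to the primary response rate or to dose selection. The first is analysed in a set that this condition does not touch, and the second rests on data with one consistent time point. The damage is confined to a sensitivity analysis and to secondary PD data, but part of it cannot be undone once samples are taken.

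**What to change.** 1. State one on-treatment sampling time in the synopsis, Sections 3.1, 7.4 and 8.2, key c and both Cycle 1 grids. The fourth dose needs the fewest edits, because the text, key c and the escalation grid already give it: the wording in Section 8.2 and one column of the expansion grid would change. The sponsor must confirm which time is intended. Also remove or explain the Week 3 Day 2 non-dosing column in the escalation grid, which carries no on-treatment PD mark.
2. Record the preceding dose number for every PD sample already taken. Summarise PD by sampling time, without pooling post-Dose 4 with post-Dose 7 samples.
3. Apply the PD-sampling condition only to the PD sensitivity analysis. Aligning the dose number alone would still make PD tissue a gate to the response-rate sensitivity set. DLBCL tumour is biopsied only where accessible, so patients would drop out of that analysis for a reason unrelated to response.

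The cost is wording in Section 8.2, the correction of the grids and one data item. No additional samples are needed.
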